8.3.2 Events of Clinical Interest

Selected non-serious and serious adverse events are also known as Events of Clinical Interest (ECI) and must be reported within 5 working days to the Sponsor and within 2 working days to Merck Global Safety. (Attn: Worldwide Product Safety; [contact]).

For the time period beginning when the consent form is signed until initiation of pembrolizumab, any ECI, or follow up to an ECI, that occurs to any subject must be reported within 5 working days to the Sponsor and within 2 working days to Merck Global Safety if it causes the subject to be excluded from the trial, or is the result of a protocol-specified intervention, including but not limited to washout or discontinuation of usual therapy, diet, placebo treatment or a procedure.

For the time period beginning at initiation of pembrolizumab through 90 days following cessation of study treatment, or 30 days following cessation of treatment if the subject initiates new anticancer therapy, whichever is earlier, any ECI, or follow up to an ECI, whether or not related to Merck product, must be reported within 5 working days to the Sponsor and within 24 hours to Merck Global Safety.

Events of clinical interest for this trial include:

1. an overdose of Merck product, as defined in Section 8.1 - Definition of an Overdose for This Protocol and Reporting of Overdose to the Sponsor, that is not associated with clinical symptoms or abnormal laboratory results.

2. an elevated AST or ALT lab value that is greater than or equal to 3X the upper limit of normal and an elevated total bilirubin lab value that is greater than or equal to 2X the upper limit of normal and, at the same time, an alkaline phosphatase lab value that is less than 2X the upper limit of normal, as determined by way of protocol-specified laboratory testing or unscheduled laboratory testing.*

*Note: These criteria are based upon available regulatory guidance documents. The purpose of the criteria is to specify a threshold of abnormal hepatic tests that may require an additional evaluation for an underlying etiology.

8.3.3 Evaluating Adverse Events

An investigator who is a qualified physician will evaluate all adverse events according to the NCI Common Terminology for Adverse Events (CTCAE), version 4.0. Any adverse event which changes CTCAE grade over the course of a given episode will have each change of grade recorded on the adverse event case report forms/worksheets.

All adverse events regardless of CTCAE grade must also be evaluated for seriousness.

Table 5 Evaluating Adverse Events

An investigator who is a qualified physician, will evaluate all adverse events as to:

V4.0 CTCAE Grading	Grade 1	Mild; asymptomatic or mild symptoms; clinical or diagnostic observations only; intervention not indicated.
	Grade 2	Moderate; minimal, local or noninvasive intervention indicated; limiting age-appropriate instrumental ADL.
	Grade 3	Severe or medically significant but not immediately life-threatening; hospitalization or prolongation of hospitalization indicated; disabling; limiting self-care ADL.
	Grade 4	Life threatening consequences; urgent intervention indicated.
	Grade 5	Death related to AE
Seriousness	A serious adverse event is any adverse event occurring at any dose or during any use of Merck product that:	
	†Results in death; or	
	†Is life threatening; or places the subject, in the view of the investigator, at immediate risk of death from the event as it occurred (Note: This does	

	
not include an adverse event that, had it occurred in a more severe form, might have caused death.); or

	
†Results in a persistent or significant disability/incapacity (substantial disruption of one's ability to conduct normal life functions); or

	
†Results in or prolongs an existing inpatient hospitalization (hospitalization is defined as an inpatient admission, regardless of length of stay, even if the hospitalization is a precautionary measure for continued observation. (Note: Hospitalization [including hospitalization for an elective procedure] for a preexisting condition which has not worsened does not constitute a serious adverse event.); or

	
†Is a congenital anomaly/birth defect (in offspring of subject taking the product regardless of time to diagnosis); or

	
Is a new cancer; (that is not a condition of the study) or

	
Is an overdose (whether accidental or intentional). Any adverse event associated with an overdose is considered a serious adverse event. An overdose that is not associated with an adverse event is considered a non-serious event of clinical interest and must be reported within 24 hours.

	
Other important medical events that may not result in death, not be life threatening, or not require hospitalization may be considered a serious adverse event when, based upon appropriate medical judgment, the event may jeopardize the subject and may require medical or surgical intervention to prevent one of the outcomes listed previously (designated above by a †).

Duration	Record the start and stop dates of the adverse event. If less than 1 day, indicate the appropriate length of time and units
Action taken	Did the adverse event cause the Merck product to be discontinued?
Relationship to test drug	Did the Merck product cause the adverse event? The determination of the likelihood that the Merck product caused the adverse event will be provided by an investigator who is a qualified physician. The investigator's signed/dated initials on the source document or worksheet that supports the causality noted on the AE form, ensures that a medically qualified assessment of causality was done. This initialed document must be retained for the required regulatory time frame. The criteria below are intended as reference guidelines to assist the investigator in assessing the

Proprietary Information of MD Anderson

2017-0057

January 9, 2019

Page 38

	likelihood of a relationship between the test drug and the adverse event based upon the available information. The following components are to be used to assess the relationship between the Merck product and the AE; the greater the correlation with the components and their respective elements (in number and/or intensity), the more likely the Merck product caused the adverse event (AE):
Exposure	Is there evidence that the subject was actually exposed to the Merck product such as: reliable history, acceptable compliance assessment (pill count, diary, etc.), expected pharmacologic effect, or measurement of drug/metabolite in bodily specimen?
Time Course	Did the AE follow in a reasonable temporal sequence from administration of the Merck product? Is the time of onset of the AE compatible with a drug-induced effect (applies to trials with investigational medicinal product)?
Likely Cause	Is the AE not reasonably explained by another etiology such as underlying disease, other drug(s)/vaccine(s), or other host or environmental factors

Relationship to Merck product (continued)	The following components are to be used to assess the relationship between the test drug and the AE: (continued)	
	Dechallenge	Was the Merck product discontinued or dose/exposure/frequency reduced? If yes, did the AE resolve or improve? If yes, this is a positive dechallenge. If no, this is a negative dechallenge.

Proprietary Information of MD Anderson

2017-0057

January 9, 2019

Page 39

		(Note: This criterion is not applicable if: (1) the AE resulted in death or permanent disability; (2) the AE resolved/improved despite continuation of the Merck product; or (3) the trial is a single-dose drug trial); or (4) Merck product(s) is/are only used one time.)
	Rechallenge	
Was the subject re-exposed to the Merck product in this study?
 
If yes, did the AE recur or worsen?
 
If yes, this is a positive rechallenge. If no, this is a negative rechallenge.
 
(Note: This criterion is not applicable if: (1) the initial AE resulted in death or permanent disability, or (2) the trial is a single-dose drug trial); or (3) Merck product(s) is/are used only one time).
 
NOTE: IF A RECHALLENGE IS PLANNED FOR AN ADVERSE EVENT WHICH WAS SERIOUS AND WHICH MAY HAVE BEEN CAUSED BY THE MERCK PRODUCT, OR IF REEXPOSURE TO THE MERCK PRODUCT POSES ADDITIONAL POTENTIAL SIGNIFICANT RISK TO THE SUBJECT, THEN THE RECHALLENGE MUST BE APPROVED IN ADVANCE BY THE U.S. CLINICAL MONITOR AS PER DOSE MODIFICATION GUIDELINES IN THE PROTOCOL.

	Consistency with Trial Treatment Profile	Is the clinical/pathological presentation of the AE consistent with previous knowledge regarding the Merck product or drug class pharmacology or toxicology?
The assessment of relationship will be reported on the case report forms /worksheets by an investigator who is a qualified physician according to his/her best clinical judgment, including consideration of the above elements.		
Record one of the following		Use the following scale of criteria as guidance (not all criteria must be present to be indicative of a Merck product relationship).

Yes, there is a reasonable possibility of Merck product relationship.	There is evidence of exposure to the Merck product. The temporal sequence of the AE onset relative to the administration of the Merck product is reasonable. The AE is more likely explained by the Merck product than by another cause.
No, there is not a reasonable possibility Merck product relationship	Subject did not receive the Merck product OR temporal sequence of the AE onset relative to administration of the Merck product is not reasonable OR there is another obvious cause of the AE. (Also entered for a subject with overdose without an associated AE.)

8.3.4 Sponsor Responsibility for Reporting Adverse Events

All Adverse Events will be reported to regulatory authorities, IRB/IECs and investigators in accordance with all applicable global laws and regulations. We will record events according to phase I trials from the table below.

Recommended Adverse Event Recording Guidelines

Attribution	Grade 1	Grade 2	Grade 3	Grade 4	Grade 5
Unrelated	Phase I	Phase I	Phase I	Phase I	Phase I
			Phase II	Phase II	Phase II
				Phase III	Phase III
Unlikely	Phase I	Phase I	Phase I	Phase I	Phase I
			Phase II	Phase II	Phase II
				Phase III	Phase III
Possible	Phase I	Phase I	Phase I	Phase I	Phase I
	Phase II	Phase II	Phase II	Phase II	Phase II

		Phase III	Phase III	Phase III	Phase III
Probable	Phase I	Phase I	Phase I	Phase I	Phase I
	Phase II	Phase II	Phase II	Phase II	Phase II
		Phase III	Phase III	Phase III	Phase III
Definitive	Phase I	Phase I	Phase I	Phase I	Phase I
	Phase II	Phase II	Phase II	Phase II	Phase II
		Phase III	Phase III	Phase III	Phase III

9.1 STATISTICAL CONSIDERATIONS

The purpose of this study is to assess the safety of treatment with pembrolizumab (two cycles) in the ‘window of opportunity’ setting for bladder cancer patients who are scheduled to undergo radical cystectomy. Secondary endpoints for efficacy and biomarker activity will be described and used to design future studies.

9.2 Endpoints

9.1.1 Toxicity for Safety Monitoring (TOX)

TOX will be monitored for an approximate 3-month treatment time interval (2 cycles/6 weeks + surgery/2 week scheduling cushion + 30 day surgical complication evaluation). A patient will be considered to have a toxicity of concern (TOX) if any of the following apply:

- Any 30-day grade 3 or higher surgical complication at least possibly related to the treatment
- Any toxicity at least possibly related to the treatment that prevents surgery
 - Note, missing surgery due to progression or withdrawal will not count as a TOX event. Rapid progression is not seen with pembrolizumab.
- Death between the start of study and the 30-day post-surgical assessment will count as long as it is toxic death at least possibly related to the pembrolizumab or surgery. Deaths clearly unrelated to treatment will not count as an event.

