5.3 Randomization or Treatment Allocation

Patients will be enrolled sequentially without randomization. According to a standardized, dose escalating, phase 2 safety design a total of 20 patients may be enrolled.

Initially 3 patients will be studied at 200 mg given at weeks 1 and 4 by IV infusion. These patients will be followed for safety assessments every 3 weeks during the treatment phase and at 30 and 90 days post-op visits during the follow-up phase. If < 2 patients in the initial cohort of 3 experience a grade >3 drug related adverse event then a subsequent cohort of 17 patients at 200 mg dose will be enrolled.

The following stopping rules will apply: if at any time ≥ 3 patients experience a drug related grade 4 adverse event including bowel perforation or any drug related grade 3 skin or gastrointestinal adverse event without clinical improvement within 2 weeks of study drug discontinuation and/or initiation of corticosteroid therapy to treat the adverse event; no additional patients will be enrolled. If any grade 3 or higher adverse event that is possibly, probably or definitely related to study drug, with the exception of any grade 3 or higher adverse events that is potentially treatable with steroids and improves to grade 1 or better within 2 weeks of steroid therapy initiation and/or study treatment discontinuation, the above stopping rule would apply. Also excluded will be grade 3 lipase elevation as this is common with this agent but is almost universally asymptomatic. Grade 4 lipase elevation will be criteria for stopping. If during monitoring, a patient is found to have disease progression within the treatment study period then this will be counted as a grade 4 toxicity event and the above stopping rule would apply. If there is a >12 week delay to surgery due disease progression, then this will be counted as a grade 4 toxicity event and the above stopping rule would apply. If a patient suffers a drug related toxicity which results in an inability to perform

radical cystectomy further study enrollment will be stopped. If there is a > 12 week delay to surgery due to a drug related toxicity in 2 or more patients, further enrollment will be stopped. Once patients have received a maximum of two doses of pembrolizumab, they will undergo surgery at approximately 6 - 8 weeks. An assessment of tumor response will not be made prior to radical cystectomy.

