9.3 Safety Interim Analyses

The safety analyses will monitor TOX as defined above using the methods of Thall et al[9]. If there is high probability that the underlying TOX rate is greater than 15%, the trial will be held

until all treated patients have completed 30 days post-surgery or gone off study prior to that time. The trial will then be stopped early if the risk of severe toxicity has been confirmed. Formally, denoting TOX probability by p_{TOX} and assuming this follows a beta (1, 1) prior distribution, the trial will be held if $\text{Prob}(p_{TOX} > 0.15 \mid \text{data}) > 0.95$. Monitoring will start once the 5th patient has been on trial for 4 weeks (at the end of the first week of cycle 2). After that, monitoring will continue monthly until the 20th patient has been followed for the full treatment period. A 6th patient will only be enrolled once there is sufficient evidence that fewer than 2 patients have TOX, i.e. ≥ 4 of the first 5 patients complete 30 days after surgery with no TOX. For the purposes of ongoing monthly trial monitoring, patients will be evaluable if they have been treated and then either have a TOX or have gone 4 weeks without TOX. Patients who are without TOX at 4 weeks, but who develop TOX later within the treatment interval will count as having a TOX at the next monthly evaluation. Stopping rules and operating characteristics were calculated in MultcLean 2.1.

Note, that since we expect enrollment of 1-2 patients per month, it is possible that monthly monitoring may allow a small overrun of patients, but this is expected to be only 1-2 additional patients at any given look.

If there are this many (or more) patients with TOX:	2	3	4	5	6
Stop the trial if there are this many (or fewer) patients who are evaluable for TOX:	5	9	13	17	20*

*Always stop with 20 patients, but if 6 or more patients have a TOX event, then pembrolizumab is unsafe for 'window of opportunity' use at this dose and schedule.

The operating characteristics of this design based on simulations are summarized in the following table. Note, since accrual will continue during monitoring, it's possible that these results underestimate the numbers of patients by 1-2 patients at the higher TOX rates.

True Prob(TOX)	Pr(stop)	Median # Pts (25%, 75%)
0.05	0.03	20 (20, 20)
0.10	0.11	20 (20, 20)
0.15	0.25	20 (16, 20)
0.20	0.43	20 (5, 20)
0.25	0.60	12 (5, 20)

0.30	0.75	7 (5, 19)
0.35	0.86	5 (5, 12)
0.40	0.93	5 (5, 8)

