9.4 Analysis Plan

TOX events will be reported with a 95% credible interval assuming a non-informative prior of beta (1,1). Specific events will also be summarized. Then all adverse events and surgical complications will be reported overall by grade, attribution, and treatment period (cycle 1, cycle 2, between the end of cycle 2 and actual surgery, 30 days following surgery). Demographic and baseline laboratory results will be summarized using descriptive and graphical statistics. Changes in markers between biopsy and surgical resection will be compared with a paired t-test or non-parametric alternative as indicated for continuous measures, and with McNemar's test for binary or ordinal measures. The numbers of patients with sufficient samples for laboratory analysis will be used to plan the numbers of patients needed for enough evaluable samples future trials. Similarly this experience will guide planning for the numbers and types of markers that can be reasonably assessed from surgical specimens in this patient population after 'window of opportunity' pembrolizumab treatment.

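### TOX, the only safety rate with an interval, omits severe drug toxicity and drug-related surgery delay when cystectomy still goes ahead, although 5.3 closes enrolment for these events

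*Combined protocol and SAP*

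**What the plan says.** The primary objective (3.1.1) is to characterise the safety profile of pembrolizumab before cystectomy. Section 9.1.1 defines TOX by three items:

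- after the operation: "Any 30-day grade 3 or higher surgical complication at least possibly related to the treatment";
- before the operation, the only item for non-fatal drug toxicity: "Any toxicity at least possibly related to the treatment that prevents surgery";
- death up to the 30-day post-surgical assessment, "as long as it is toxic death at least possibly related to the pembrolizumab or surgery".

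It adds that "missing surgery due to progression or withdrawal will not count as a TOX event". The second item has no grade criterion and no delay criterion.

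Section 5.3 (in part also 2.1.1) has its own rules for closing enrolment. One applies "if at any time ≥ 3 patients experience a drug related grade 4 adverse event including bowel perforation"; the same rule covers unresolved drug-related grade 3 skin or gastrointestinal events. Another concerns late surgery: "> 12 week delay to surgery due to a drug related toxicity in 2 or more patients, further enrollment will be stopped". A third, listed separately, applies when drug toxicity makes cystectomy impossible in one patient.

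The inference in Section 9 uses TOX only. The hold rule and boundary in 9.3 are TOX counts, and the footnote gives the safety conclusion: "if 6 or more patients have a TOX event, then pembrolizumab is unsafe for" (the sentence then names the setting and regimen). In 9.4, "TOX events will be reported with a 95% credible interval assuming a non-informative prior of beta (1,1"). All adverse events and surgical complications are then tabulated by grade, attribution and treatment period. Section 9 does not mention the 5.3 rules.

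**The concern.** The protocol holds two working definitions of unacceptable drug toxicity, and only the narrower one reaches the estimated rate and the stated safety conclusion. A patient with a drug-related grade 4 event who is later operated on without a related complication counts towards closing enrolment but is a non-event in the TOX rate.

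At stake is how the primary question is answered. A trial closed under 5.3 for drug toxicity could report a TOX estimate that contains none of the events that closed it. Delay of cystectomy caused by the drug is a harm specific to this setting, yet neither its frequency nor its length is a planned summary.

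The point concerns the final estimate and conclusion, not the calculation of the TOX stopping probabilities.

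**Working it through.** **Inputs.** Beta(1,1) prior, 15% limit, 0.95 cut-off and boundary table (9.3); N = 20 and the interval for 3/20 (9.2); TOX items (9.1.1); enrolment stops (5.3). The documents give no expected rate for severe drug toxicity that still allows surgery, so the event counts below are assumptions.

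**Formula.** With x events in n patients, the posterior is Beta(1+x, 1+n−x). The interval runs from its 2.5% to its 97.5% quantile, and a hold requires P(rate > 0.15) > 0.95.

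**The plan's own figures.** For 3/20, Beta(4,18) gives 5.45% to 36.34%; 9.2 states 5.4% to 36.3%. The smallest count meeting the cut-off is 2 at n = 5, 3 up to n = 9, 4 up to 13, 5 up to 17 and 6 up to 20, as in the 9.3 table. An exact recursion with a look after each patient from 5 to 19 gives Pr(stop) of 0.027, 0.113, 0.255, 0.429, 0.605, 0.753, 0.862 and 0.931 at true rates 0.05 to 0.40, all within one point of that table. These results depend on TOX counts alone, so a 5.3 event that is not TOX changes none of them.

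**Definitions side by side, when surgery takes place with no related grade 3+ complication or toxic death**

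| Event | TOX (9.1.1) | Counts towards a 5.3 stop |
|---|---|---|
| Drug-related grade 4 event | No | Yes, 3 or more patients, subject to the exception below |
| Unresolved drug-related grade 3 skin/GI event | No | Yes, 3 or more patients |
| Drug-related delay over 12 weeks | Not stated | Yes, 2 or more patients |

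**Illustration 1.** Three drug-related grade 4 events in the first 6 patients, none within 5.3's exception for steroid-treatable events that improve to grade 1 or better within 2 weeks, and all followed by uneventful surgery. With events in patients 3, 5 and 6, for example, this is compatible with the three-patient lead-in in 5.3 (one event) and the five-patient gate in 9.3 (no TOX). The third event closes enrolment under 5.3.

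- As written, 0/6, Beta(1,7): lower limit 1 − 0.975^(1/7) = 0.4%, upper limit 1 − 0.025^(1/7) = 41.0%, P(rate > 15%) = 0.85^7 = 0.32.
- Counted, 3/6, Beta(4,4): 18.4% to 81.6%. P(rate > 15%) = P(Bin(7, 0.15) ≤ 3) = 0.321 + 0.396 + 0.210 + 0.062 = 0.99. The boundary of 3 in 9 or fewer is crossed.

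**Illustration 2.** Two drug-related delays over 12 weeks in the first 5 patients, both eventually operated on without complication. Enrolment closes under 5.3.

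- If delay is not prevention: 0/5, 0.4% to 45.9%, P(rate > 15%) = 0.85^6 = 0.38.
- If it is: 2/5, 11.8% to 77.7%, P = 0.953, which crosses the boundary.

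The TOX window is 6 weeks + 2 weeks + 30 days = 86 days. Planned surgery is at weeks 6 to 8, so a delay of more than 12 weeks from then puts surgery after week 18 to 20, outside the window. Section 9.1.1 does not say whether that counts as preventing surgery.

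**Range for the assumption.** If such events occur independently at 5%, 10%, 15% or 20% per patient, the chance of three or more among 20 patients is 0.08, 0.32, 0.60 or 0.79.

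**The case against.** The strongest reply is that TOX is labelled as a safety-monitoring measure and asks whether the drug harms surgery, while 5.3 covers general drug toxicity. Section 2.1.1 points to 5.3 for additional rules, so layering is intended. Adverse events are a separate endpoint (9.1.2), recorded at every grade and attribution (8.3.4) and tabulated in 9.4, including for the period between cycle 2 and surgery. That stands, and a reader who inferred that severe drug toxicity would go unreported would be wrong. What is missing is a per-patient proportion with an interval, any summary of delay, and a link to the safety conclusion.

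A reader might also infer that such a trial would report a reassuring rate, or that counting the events would always change the conclusion. Neither is supported. An upper limit of 41.0% for 0/6 is not reassuring. If enrolment closed at patient 12 instead, 0/12 gives 0.2% to 24.7% with P(rate > 15%) = 0.12. Counted, 3/12 gives 9.1% to 53.8% with P = 0.88, below the 0.95 cut-off. Three events are also short of the six in the 9.3 footnote.

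A further objection is that a long delay could be read as preventing surgery within the roughly 3-month window. The text allows this, although 5.3 lists delay and inability separately. It is a reason to clarify 9.1.1, and it does not touch the grade 4 gap.

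Finally, 5.3 is not fully clear itself. One sentence counts drug-related grade 4 events, while the next exempts some grade 3 or higher events that improve on steroids. It also counts progression as a grade 4 toxicity event, whereas 9.1.1 excludes surgery missed because of progression. A combined measure cannot be computed until these are settled.

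**Conclusion.** The point holds as a gap in the final analysis. By definition, drug-related grade 4 events and unresolved grade 3 events fall outside TOX when surgery follows uneventfully, and drug-related delay has no planned summary and an unclear TOX status. This needs no assumed event rate. The size does: in the six-patient illustration the headline moves from 0/6 (P(rate > 15%) = 0.32) to 3/6 (P = 0.99), which rests on three assumed events, none within the steroid exception. With later closure, as at patient 12, the interval shifts but no boundary is crossed.

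The documents do not support the stronger inferences that toxicity is concealed, that the TOX operating characteristics in the 9.3 table are wrong, or that the unsafe statement would generally be reversed. The change is worth making because it bears on the primary objective and costs little.

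**What to change.** Before the analysis is fixed, the sponsor should reconcile three points; no view is taken here on which rule is right:

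- which grade 3 and 4 events count under 5.3;
- the opposite treatment of progression in 5.3 and 9.1.1;
- whether a delay beyond the window counts as preventing surgery, and from which date delay is measured.

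Then, leaving TOX, its 15% boundary and all enrolment rules unchanged:

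1. In 9.4, add over all treated patients the proportion with TOX or any drug-related event counting towards a 5.3 stop, with the same Beta(1,1) 95% credible interval. Leave disease progression out of this proportion and report it separately.
2. In 9.4, report the number of patients with drug-related surgery delay and its length in days.
3. In the 9.3 footnote, state that the safety conclusion also reports whether a 5.3 stop was triggered.

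The cost is the reconciliation, some wording, one more proportion and a short delay summary. Adverse events are already collected from first dose to 30 days after surgery (8.1), and surgery is a scheduled event in the flow chart. The downside for the sponsor is that the added figure can only equal or exceed the TOX rate, so the headline can only become less favourable.

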5.8 Subject Withdrawal/Discontinuation Criteria

Subjects may withdraw consent at any time for any reason or be dropped from the trial at the discretion of the investigator or treating physician should any untoward effect occur. In addition, a subject may be withdrawn by the principal investigator if enrollment into the trial is inappropriate, the trial plan is violated, or for administrative and/or other safety reasons.

A subject must be discontinued from the trial for any of the following reasons:

- The subject or legal representative (such as a parent or legal guardian) withdraws consent
- Unacceptable adverse experiences as described in Table 3 and section 5.6.1
- Unexpected intercurrent illness that prevents further administration of study treatment
- Investigator's decision to withdraw the subject
- The subject has a confirmed positive serum pregnancy test
- Noncompliance with study treatment or procedure requirements
- The subject is lost to follow-up: two failed attempts to contact the patient by phone or e-mail AND one unanswered certified letter sent to subject's registered home address.
- Completed study participation or of follow up from initiation of study treatment.

Subjects who prematurely discontinue from the study treatment, will return to clinic within 30 days of treatment discontinuation to complete the safety assessments listed under the

“Early Treatment Discontinuation” visit listed in Section 6. All other subjects will continue on the follow-up phase through 90 days post-op.

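### The 9.1.1 note exempts surgery missed through withdrawal whatever the reason, so withdrawal caused by related toxicity can be scored as TOX-free

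*Combined protocol and SAP*

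**What the plan says.** Section 9.1.1 defines TOX by three limbs: a related grade 3 or higher surgical complication within 30 days, a related toxicity that stops surgery from taking place, and a related toxic death. The second limb reads "Any toxicity at least possibly related to the treatment that prevents surgery". A note nested under it states that "missing surgery due to progression or withdrawal will not count as a TOX event". The note puts no condition on the reason for withdrawal.

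Section 5.8 lists the ways a subject can leave the trial, and several are adverse effects:

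- A subject may "be dropped from the trial at the discretion of the investigator or treating physician should any untoward effect occur".
- The principal investigator may withdraw a subject if "the trial plan is violated, or for administrative and/or other safety reasons" apply.
- Discontinuation is mandatory for "Unacceptable adverse experiences as described in Table 3 and section 5.6.1".

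For the denominator, Section 9.3 says that "patients will be evaluable if they have been treated and then either have a TOX or have gone 4 weeks without TOX". Section 9.4 reports the TOX rate with a 95% credible interval under a beta(1,1) prior. Section 9.3 uses the same count for the stopping boundary and for the conclusion, at 6 or more of 20, that the drug is unsafe in this setting.

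**The concern.** Safety is the primary objective, and TOX is the only safety rate for which the plan gives a credible interval and a decision rule. Withdrawal in this trial is not independent of toxicity, because Section 5.8 makes toxicity a reason for it. If a patient has a related toxicity, withdraws or is withdrawn, and does not have surgery, 9.1.1 gives two answers. The second limb makes the patient an event. The note makes the same patient a non-event. No section says which governs.

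The ambiguity works in one direction. The note can only remove events; it cannot add any. Under 9.3 a treated patient who passed 4 weeks without TOX is already evaluable, so the removed event does not leave the denominator but becomes a success. The same records could therefore give two TOX rates, depending on who codes the missed surgery.

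**Working it through.** **Inputs.** N = 20 (Section 9.2). Threshold 15%, prior beta(1,1), posterior cut-off 0.95, and boundary 2/5, 3/9, 4/13, 5/17, 6/20 (Section 9.3). The documents give no rate of toxicity-driven withdrawal, so the check is the effect of reclassifying one patient.

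**Formula.** With k events in n evaluable patients, the posterior is Beta(1+k, 1+n−k). The decision quantity is P(p > 0.15) under that posterior. The credible interval runs from its 2.5% to its 97.5% quantile.

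**Reproducing the plan.**

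- Interval at 3/20: Beta(4, 18) gives 5.4% to 36.3%, as stated in Section 9.2.
- Boundary: P(p > 0.15) is 0.953 at 2/5, 0.950 at 3/9 (just above the cut-off), 0.953 at 4/13, 0.958 at 5/17 and 0.971 at 6/20. All five points agree with the 9.3 table.
- Stopping probability, by exact binomial recursion with a look after each patient from 5 to 19: 0.255 at a true rate of 15% and 0.753 at 30%, against 0.25 and 0.75 in the 9.3 table.

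**One patient scored each way.** One patient is 1/20 = 5 percentage points, a third of the 15% threshold (5/15).

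| TOX count | Rate | Posterior | 95% credible interval | P(p > 0.15) |
|---|---|---|---|---|
| 3/20 | 15% | Beta(4, 18) | 5.4% to 36.3% | 0.611 |
| 4/20 | 20% | Beta(5, 17) | 8.2% to 41.9% | 0.803 |
| 5/20 | 25% | Beta(6, 16) | 11.3% to 47.2% | 0.917 |
| 6/20 | 30% | Beta(7, 15) | 14.6% to 52.2% | 0.971 |

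The cut-off of 0.95 lies between the last two rows. A trial with five undisputed events and one disputed withdrawal is below the unsafe criterion under the note and meets it under the second limb.

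Taking the disputed patient out of the denominator does not settle the matter. 5/19 gives Beta(6, 15) and P(p > 0.15) = 0.933, still below 0.95. The classification rule itself has to be fixed.

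**Which events are exposed.** Surgical complications need surgery to have taken place, and related deaths have their own limb. The note can remove neither. Only events under the second limb can be lost.

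**The case against.** The best defence is that the note should be read with the bullet it sits under. On that reading, surgery missed because of related toxicity is TOX, and the note only lists reasons that are not toxicity. This is tenable, and it is why the loss is possible rather than certain. It does not resolve the conflict: the note is the more specific text, withdrawal for toxicity is an ordinary route in Section 5.8, and the death limb of the same list does state a relatedness condition where this note states none.

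Three other points stand in part:

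- Section 5.3 stops enrolment if a single patient has a drug-related toxicity that makes cystectomy impossible. That is stricter than any TOX boundary. It does not feed the TOX rate or its interval, and it may not be triggered when the recorded reason is withdrawal.
- Leaving the trial need not mean missing cystectomy, which was already planned. A patient who still has surgery is outside the note.
- Section 9.4 reports all adverse events by grade, attribution and period, so the toxicity itself would be visible. That listing does not correct the TOX count.

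A reader might infer that one miscoded withdrawal could also reverse the first look, by turning 2/5 into 1/5. The documents do not support this. Section 9.3 admits a 6th patient only when at least 4 of the first 5 have completed 30 days after surgery without TOX. With one TOX and one withdrawal without surgery, only 3 of 5 qualify, however the withdrawal is coded.

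A reader might also apply an assumed loss to all TOX events and quote a fall in the stopping probability. That uses the wrong base, because only second-limb events are exposed and the documents do not give their share.

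**Conclusion.** The concern holds as an unresolved conflict within the key safety endpoint. A missed surgery that follows toxicity-driven withdrawal can be scored either way, and the scoring allowed by the note can only lower the rate. Each affected patient in 20 is worth 5 points. At 5 against 6 events, one patient decides the unsafe verdict (0.917 against 0.971).

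These sizes assume a full cohort of 20 evaluable patients. They also assume at least one patient whose surgery was missed because of related toxicity and was recorded as a withdrawal, and that the 5.3 stop did not end accrual first. How often this would happen cannot be estimated from the documents. It would go too far to say that the plan does discard such events, or that the TOX rate covers only patients who reached surgery. The second limb may be read as governing, and the second and third limbs both count patients who never had surgery. The matter should be corrected before the data are read, but it does not invalidate the design.

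**What to change.** In Section 9.1.1, limit the withdrawal part of the note. Suggested text: *Surgery missed through withdrawal is not a TOX event when the reason for withdrawal was something other than toxicity at least possibly related to treatment. Surgery missed because of such toxicity is a TOX event under the second bullet, whoever initiated the withdrawal.* Require the reason for every missed surgery to be recorded. The test should be that the toxicity caused the missed surgery. A rule that counted any ongoing related event at withdrawal, of whatever grade, would go beyond the second bullet and push the rate upward.

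In Section 9.4, report TOX on all treated patients under this rule. Add one sensitivity line that removes the remaining treated patients without cystectomy from the denominator.

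The cost is a few sentences, one recorded item per missed surgery and one extra table line. The TOX rate may come out slightly less favourable, and attributing the reason for a withdrawal will need some judgement.
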